### 4. Exploratory subgroup analyses:

4.1. Compare diabetes vs non-diabetes status groups separately.

# 5. Pre-specified post-hoc analyses:

We will determine the acute and chronic effects of dapagliflozin vs. placebo from baseline on:

- 5.1. Urine adenosine
- 5.2. Whether changes in proximal renal tubular natriuretic effect are associated with changes in afferent arteriolar tone.

## **INFINITI Data Analysis Plan**

## **Outcomes**

### 1. Outcomes for the primary objective:

- 1.1. The primary outcome is measured by the acute and chronic change in seated systolic blood pressure (measured using automated sphygmomanometer) from baseline with dapagliflozin vs placebo.
- 1.2. We will also measure the primary objective on these secondary outcomes:
  - a. Seated diastolic blood pressure
  - b. Seated mean arterial pressure

#### 2. Outcomes for the secondary objectives:

- 2.1. Safety will be assessed by the number of hypoglycemic episodes, acute rejection episodes, volume depletion, UTI or genital infection, acute kidney injury, ketoacidosis and serious adverse events.
- 2.2. CNI levels will be measured by tacrolimus or cyclosporine levels
- 2.3. Systemic hemodynamic assessments include the following group of outcomes:
  - a. NICOM parameters (chronic change only)
  - b. arterial stiffness
    - *i.* radial, aortic and carotid augmentation index (AIx)
    - *ii.* carotid-radial pulse-wave velocity (PWV)
    - iii. carotid-femoral PWV
- 2.4. Natriuretic effect will be measured using the following group of outcomes:
  - a. Lithium clearance
    - *i.*  $FE(Li^+) = 100 X ([(urine Li^+) X (creatinine plasma)]/[(plasma Li^+) X (creatinine urine)]$
  - b. Total overall (proximal and distal) tubular sodium handling
    - *i.*  $FE(Na^+) = 100 X ([(urine Na^+) X (creatinine plasma)]/[(plasma Na^+) X (creatinine urine)]$
  - c. Distal sodium handling:
    - $i. \quad FE(Na^+) FE(Li^+)$
- 2.5. SNS activation will be measured by norepinephrine, epinephrine, dopamine, heart rate and heart rate variability (RMSSD and SDNN).
- 2.6. Metabolic parameters will be measured by weight and waist circumference Lipid profile will be measured by cholesterol, LDL, HDL and triglyceride (use screening instead of baseline value).
- 2.7. Renal hemodynamic function will be measured using the following groups of outcomes:
  - a. Iohexol measured GFR
    - i. mGFR
    - *ii. Hematocrit (HCT)*
  - b. 24 hour urine measured GFR
    - *i.* 24-hour Creatinine (mmol/day)
    - *ii.* Creatinine clearance (ml/min)
  - c. Estimated GFR (eGFR) calculated by CKD-EPI 2021 equation
- 2.8. Neurohormones will be measured by plasma aldosterone and plasma renin concentration

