2.4 SGLT2 inhibitors in kidney transplant recipients: Special considerations

Given the glucose-dependent and independent effects of SGLT2i, as well as the accumulating evidence demonstrating cardiorenal protection in non-KTR, the use of these agents in KTR is attractive - especially since traditional renin-angiotensin-aldosterone system inhibitors are not effective. Moreover, the use of SGLT2i as a cardiorenal protective therapy may be of particular value in KTR given the high burden of comorbidities such as diabetes, CVD and hypertension, as well as the ongoing challenges of premature death and graft loss in this population. However, there are several unique aspects of KTR that are important to consider when using SGLT2i, including the immunosuppressed state of KTR, the impact of SGLT2i on denervated kidneys as well as the effectiveness of SGLT2i with concomitant use of CNIs. Given the susceptibility of KTR to infectious complications due to immunosuppression, there is the potential for concern regarding safety of these agents in this population. For example, urinary and mycotic infections are well described with SGLT2i use^{57, 58}, and urinary tract infections are one of the most common infectious complications in KTR^{59, 60}. In addition, transplanted kidneys are denervated and therefore the autoregulation of renal blood flow that occurs in the setting of sympathetic nervous system activity, particularly when hypotension occurs, is attenuated⁶¹. SGLT2i can cause volume depletion and acute kidney injury (AKI), and it is unclear whether these adverse effects are magnified in KTR with denervated kidneys. Finally, CNIs are commonly used in almost all KTR, and are well known to affect the kidnev⁶². In particular, CNIs can result in tubular toxicity through a variety of mechanisms including hypoxia of the tubulointersitium, apoptosis of tubular cells and alterations in tubular transport, as manifested by well-described electrolyte disturbances^{15, 62}. In non-KTR, SGLT2i therapies are very safe over a wide range of kidney function and have even been shown to reduce the risk of AKI. Thus, an important aim of our study is to capture potential safety signals, including infectious complications and changes in renal function in the KTR population.

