3.3 Anticipated Outcomes

- 1. We hypothesize that dapagliflozin will result in a significant reduction in systolic and diastolic blood pressure in a cohort of KTR with or without T2D and PTDM.
- 2. We hypothesize that dapagliflozin will be well tolerated in KTR with or without T2D and PTDM, with adverse events similar to that of non-transplant populations. We also hypothesize that there will be no clinically significant changes in CNI levels or episodes of acute rejection in KTR treated with dapagliflozin vs. placebo during the study.
- 3. We hypothesize that dapagliflozin will result in a significant natriuresis, as well as reductions in arterial stiffness, albuminuria, allograft hypoxia and markers of oxidative stress, while having neutral effects on cardiac and renal function over the course of the 12-week study period.
- 4. We hypothesize that the glucose-lowering effects of dapagliflozin will be modest in KTR with T2D or PTDM due the high prevalence of CKD in this population. In participants without T2D or PTDM, we do not expect any glucose lowering.

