5.3 Sample Size

The sample size is based on the primary endpoint of blood pressure. Currently, there is only one publication from our group with information available on the effect of SGLT2i on blood pressure reduction in KTR with diabetes. In this observational study of 10 KTR and simultaneous pancreas-kidney transplant recipients treated with canagliflozin, we reported a SBP decrease of $6.5 \pm 10 \text{ mmHg}^{63}$. Given the small sample size in our observational study, we believe the standard deviation would be smaller in a larger cohort. Blood pressure reduction with SGLT2 inhibition appear to be similar between patients with and without diabetes in non-transplant studies. We, therefore, estimated the sample size based on a SBP change of 6.5 mmHg with a standard deviation of 8 mmHg. Under the hypothesis that SGLT2i decreases SBP by $6.5 \pm 8 \text{ mmHg}$ compared to placebo with a two-sided alpha of 0.05 and 80% power, we calculate a sample size of n=48, with 24 randomized to dapagliflozin and 24 randomized to placebo. Assuming a 10% attrition rate, the final sample size required is 52 participants. This sample size is similar to those successfully used in previous studies⁷¹, and sufficient to measure secondary renal endpoints related to renal hemodynamic function⁷¹, natriuresis and arterial stiffness⁷²⁻⁷⁴. Based on previous studies, we anticipate an even sex distribution in each group.

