7.6.1 Potential risks

The potential risks for the treatment with dapagliflozin and other SGLT2 inhibitors are described in the IB. Due to its mode of action resulting in increased urinary glucose excretion an increased risk of urinary tract infections (slightly higher compared to placebo in the phase III studies) and genital infections has been seen.

Based on the mechanism of action of dapagliflozin there may be a potential risk for this compound to cause hypovolaemia or electrolyte imbalance. As a precaution, patients who, in the judgment of the Investigator may be at risk for dehydration or volume depletion due to co-existing conditions or concomitant medications, such as loop diuretics, should have careful monitoring of their volume status. In patients already receiving dapagliflozin who develop conditions that may cause hypovolaemia or electrolyte imbalance, decisions to interrupt or discontinue dapagliflozin therapy and management of patients should be based on clinical judgment.

Higher proportions of patients with marked laboratory abnormalities of hyperphosphatemia were reported in dapagliflozin vs placebo. The magnitude and clinical significance of this in patients with CKD is unclear.

After the introduction of dapagliflozin and other SGLT2 inhibitors there have been post marketing reports of ketoacidosis, including diabetic ketoacidosis (DKA), in patients with type 1 diabetes (T1D) and T2D, although a causal relationship has not been established. Patients presenting signs and symptoms consistent with ketoacidosis, including nausea, vomiting, abdominal pain, malaise, and shortness of breath, should be assessed for ketoacidosis, irrespective of blood glucose levels. If ketoacidosis is suspected, discontinuation or temporary interruption of dapagliflozin should be considered and the patient should be promptly evaluated.

Predisposing factors to ketoacidosis include a low beta-cell function reserve resulting from pancreatic disorders (e.g., T1D, history of pancreatitis, or pancreatic surgery), insulin dose reduction, reduced caloric intake, or increased insulin requirements due to infections, illness or surgery and alcohol abuse. Dapagliflozin should be used with caution in these patients.

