10.2.3 Adverse events of interest

Urinary tract infections

Genital infections

Diabetic ketoacidosis (DKA)

Volume depletion (Eg, dehydration, hypovolemia, or hypotension)

Fractures

Major hypoglycaemic event

A major hypoglycaemic event is defined as an event that requires assistance of another person to actively administer carbohydrates, glucagon, or take other corrective actions. Plasma glucose concentrations may not be available during an event, but neurological recovery following the corrective actions is considered sufficient evidence that the event was induced by a low plasma glucose concentration.

Acute Kidney Injury

Acute kidney injury is defined as an increase of 40% in serum creatinine from the previous visit or hospitalization due to acute kidney injury.

Amputation:

Amputations will be recorded in the eCRF. We will report the underlying cause of amputation as the AE and include the information regarding the actual amputation in the AE description rather than reporting the amputation procedure as a separate AE.

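### SAP 2.1 lists urinary tract and genital infections as one safety item, with no counting rule and no interval, although the protocol keeps the two apart

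*SAP*

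**What the plan says.** The SAP names the safety outcomes under Outcomes, item 2.1: "Safety will be assessed by the number of hypoglycemic episodes, acute rejection episodes, volume depletion, UTI or genital infection, acute kidney injury". The list then closes with two further entries, one for serious adverse events and one for ketoacidosis. Item 2.1 of the SAP's analysis section repeats it with the same joined infection entry. It asks for the numbers in each arm and rules out statistical comparison. No percentage, denominator, interval or participants-versus-events rule is given. SAP section 4 splits the adverse event counts by diabetes status, but nothing splits them by type of infection.

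The protocol is finer. Section 10.2.3 gives "Genital infections" an entry of its own, after a separate entry for urinary tract infections. Table 3 collects urinary infections and mycotic infections as separate variables. The two are also described differently. Section 2.4 says that "urinary tract infections are one of the most common infectious complications in KTR", and section 7.6.1 reports that "an increased risk of urinary tract infections (slightly higher compared to placebo in the phase III studies) and genital infections has been seen".

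Safety is the first secondary objective (protocol 3.2). Section 2.4 makes the capture of safety signals, infections included, an important aim. Section 3.3 expects that "dapagliflozin will be well tolerated in KTR with or without T2D and PTDM, with adverse events similar to that of non-transplant populations", with no criterion or margin attached. Protocol section 11 likewise plans tabulation of adverse event frequencies without comparison.

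**The concern.** Two infections with different background frequency and different described drug risk share one planned number. If that number is produced as written, a difference in genital infections is added to a common event that occurs in both arms. The planned table then becomes a weak place to look for one of the infectious signals that the protocol wants to capture in immunosuppressed patients.

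Two further gaps sit in the same item. First, without a counting rule, two analysts could produce different figures from the same data. If events are counted, one participant with recurrent urinary infection can move the total. Second, a bare count in an arm of about 26 carries no sign of how little it excludes. This matters most for the rarer items, such as acute rejection and ketoacidosis, where zero is a plausible result.

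**Working it through.** **1. Denominator.** The documents give no figure for the safety counts, so the sample size for systolic pressure fixes them. Protocol 5.3 "estimated the sample size based on a SBP change of 6.5 mmHg with a standard deviation of 8 mmHg", "compared to placebo with a two-sided alpha of 0.05 and 80% power". The normal-approximation formula gives n per arm = 2 × (1.960 + 0.842)² × (8/6.5)² = 23.8, so 24. This reproduces the plan: "we calculate a sample size of n=48, with 24 randomized to dapagliflozin and 24 randomized to placebo". (The t-based value is 24.8, so 25.) The plan then allows 10% attrition and states 52 in total, or 52/2 = 26 per arm. Protocol 9.6 allows new patients to be admitted after a withdrawal, so the actual arms need not be exactly 26.

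**2. What zero events exclude.** With no events in n participants, the exact (Clopper-Pearson) two-sided 95% upper limit is 1 − 0.025^(1/n).
- n = 26: 1 − 0.025^(1/26) = 13.2%.
- n = 24: 1 − 0.025^(1/24) = 14.2%.

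The chance of seeing no events in 26 is (1 − p)^26. It is 26.4% at a true risk of 5% and 6.5% at 10%. Counts within diabetes subgroups rest on fewer participants and exclude less.

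**3. Dilution from pooling.** The documents give no rate of either infection for this trial. Protocol Table 1 offers only small series on drug with differing follow-up: 0 urinary infections in 10 patients, 2 episodes in 10, 1 in 8 and 5 in 14. The rates below are therefore assumptions, shown as a range. Take genital risk g as 10% on drug and 1% on placebo, urinary risk u equal in both arms, the two independent, and participants counted. The pooled risk is 1 − (1 − g)(1 − u). At u = 10%, for example, it is 1 − 0.90 × 0.90 = 19.0% on drug and 1 − 0.99 × 0.90 = 10.9% on placebo. The last two columns come from a simulation of 400,000 trials with 26 per arm.

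| Item | Drug | Placebo | Risk ratio | Difference (points) | Drug count higher | Drug count lower |
|---|---|---|---|---|---|---|
| Genital alone | 10.0% | 1.0% | 10 | 9.0 | 88.5% | 2% |
| Pooled, u = 5% | 14.5% | 5.95% | 2.44 | 8.55 | 79.0% | 9.8% |
| Pooled, u = 10% | 19.0% | 10.9% | 1.74 | 8.1 | 73.7% | 15.1% |
| Pooled, u = 20% | 28.0% | 20.8% | 1.35 | 7.2 | 67.3% | 22.0% |

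With genital risks of 5% and 1%, the ratio falls from 5 to 1.64, 1.33 and 1.15. The chance that the drug arm shows the higher count falls from 65% to 60%, 57% and 54%.

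Most of the absolute difference survives pooling. What is lost is contrast against a noisier background.

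**4. What this looks like in counts (assumed, distinct participants).** Genital infection in 3 vs 0 of 26, with urinary infection in 2 vs 4, pools to 5 vs 4. Genital infection in 4 vs 0, with urinary infection in 5 vs 5, pools to 9 vs 5. In the second case the excess of 4 is still there.

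**The case against.** The strongest reply is that nothing is lost. The protocol records the infections separately (10.2.3 and Table 3), prefers diagnoses to lists of symptoms (10.3), and commits separately to tabulating adverse event frequencies (section 11). The line can be split at any time. The SAP defines no composite and shows no table shell, and its joined wording may be shorthand for two rows; item 2.2 joins tacrolimus and cyclosporine in the same loose way. Descriptive safety reporting without tests is sensible with 52 participants over 12 weeks.

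Most of this stands. A reader might infer that a genital signal would be hidden. The documents do not support that: the data remain separable, and pooling dilutes the excess without removing it. Nor is urinary infection pure background, since protocol 7.6.1 reports a slight increase on drug. The same section gives no size for the genital excess, so the documents do not establish genital infection as the contrast most likely to show a drug effect. Nor does the SAP say that infections are counted as episodes; it attaches that word to hypoglycemia and acute rejection. Even 4 vs 0 of 26 is not strong evidence alone (two-sided Fisher p = 0.11).

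What does not fall away is that the SAP uses the joined item in two places, nowhere says that two rows are meant, and is coarser than the protocol's own list without giving a reason. It also leaves the counting unit open. A reader who knows the arm size can derive an exact limit only if participants are counted.

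**Conclusion.** The point holds as a weakness of the planned safety summary. Read literally, SAP 2.1 departs from the protocol's separate adverse events of interest and would dilute a difference in genital infections. At 5% background urinary infection the loss is modest; at 20% a tenfold ratio reads as about 1.35. These figures rest on assumed risks, independence of the two infections and equal urinary risk in both arms. The missing counting rule and the missing intervals need no such assumptions: 0 of 26 leaves a true risk of up to 13.2% open, and 0 of 24 up to 14.2%.

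A reader might go further and infer that zero counts will be taken as evidence of safety. No passage says so. The SAP's objective is to characterize safety, comparisons are ruled out, and the tolerability hypothesis in protocol 3.3 carries no criterion. The limits above are a reason to show the uncertainty, not proof of an intended misreading. The primary analysis and the sample size are unaffected.

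**What to change.** Amend SAP item 2.1 in both the Outcomes and the analysis section:

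- Report urinary tract infection and genital infection on separate lines, in keeping with protocol 10.2.3.
- For each safety outcome give, per arm, the participants with at least one event (n/N, %), the total number of events, and the exact 95% confidence interval for the proportion.
- When an arm has no events, report the upper limit beside the zero.
- Keep the rule of no hypothesis tests.

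The data are already collected, so the change is SAP wording and table layout. The cost is a slightly longer table and wide intervals that make the safety statement less favourable.

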There are no known or reported drug interactions with dapagliflozin and immunosuppressive therapies commonly used in KTR including CNIs (tacrolimus, cyclosporine), mammalian target of rapamycin inhibitors (sirolimus, everolimus), antiproliferative medications (mycophenolic acid, mycophenolate mofetil, azathioprine) and prednisone. SGLT2i are primarily metabolized via UDP-glucoronosyltransferase, with minimal effects on cytochrome P450 enzymes. CNIs are substrates of these enzymes, however the interaction does not appear to be clinically relevant⁶³. CNI levels will be monitored for the duration of this trial and will be reported to the participants' primary transplant nephrologist within 24 hours for CNI dose adjustments, as needed. There will be no change required to the general management of KTR as a result of participation in the study.

Study medication is received at the study site by a designated person, handled and stored safely and properly, and kept in a secured location. The study medication will be stored according to the instructions specified on the drug labels. Storage conditions are adequately monitored. Subjects are asked to return all unused study drug and packaging at the end of the study or at the time of study drug discontinuation or in every visit to the outpatient clinic. Appropriate documentation of

the subject specific dispensing process is maintained. Unused drugs are destroyed by the pharmacy department at the end of the study.

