## 2. Secondary objectives:

2.1. We will characterize the safety of dapagliflozin use compared to placebo.

We will determine acute and chronic effects of dapagliflozin vs. placebo from baseline on:

- 2.2. Calcineurin inhibitors (CNI) levels, a class of immunosuppressants measured by tacrolimus or cyclosporine
- 2.3. Systemic hemodynamics
- 2.4. Total and proximal renal tubular natriuresis measured by sodium/lithium clearance
- 2.5. Sympathetic nervous system (SNS) activation
- 2.6. Metabolic parameters
- 2.7. Kidney function indicated by iohexol-measured and estimated glomerular filtration rate (GFR)
- 2.8. Neurohormones
- 2.9. Glucose-lowering effects

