# 1. Analysis for the primary objective:

- 1.1. To assess dapagliflozin-related acute and chronic changes in the primary outcome of seated systolic blood pressure compared to placebo, linear mixed-effects models will be used. Two separate models will be fit. For acute change, the vector of outcomes will include the baseline and 1-week values (i.e. Visit 3 and Visit 4 values). For chronic changes, the vector of outcomes will include the baseline and 12-week values (i.e. Visit 3 and Visit 9 values). The covariates will include the visit and treatment-by-visit interaction; due to randomization, a covariate for the main effect of treatment will not be included. The treatment-by-time coefficient, its 95% confidence interval, and its p-value will be used to assess the effect of treatment.
- 1.2. We will repeat this analysis with:
  - a. Seated diastolic blood pressure as an outcome
  - b. Seated mean arterial pressure as an outcome

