# 2. Analysis for secondary objective:

- 2.1. The numbers of hypoglycemic episodes, acute rejection episodes, volume depletion, UTI or genital infection, acute kidney injury, ketoacidosis and serious adverse events will be reported for both the placebo group and dapagliflozin group. No statistical comparisons will be performed.
- 2.2. 2.10. The same models described in the analysis of primary objective 1.1 will be completed for each of the different outcomes.

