#### 5. Pre-specified post-hoc analyses:

- 5.1. The same models described in the analysis of primary objective 1.1 will be performed for the outcome.
- 5.2. The same models described in the analysis of exploratory objective 3.2 will be completed for each of the different outcomes.

Analysis population: The intention to treat population will be used for all analyses.

*Hypothesis testing:* For hypothesis testing, a 5% significance level will be used (two-sided). No interim analyses will be performed. For secondary objectives, nominal p-values will be reported.

*General model assumptions and model diagnostic procedures:* For the linear mixed-effects models with visit and treatment-by-visit interaction as covariates, a participant-level random intercept will be included. Restricted-maximum-likelihood will be used for estimation and the missing-at-random framework will be assumed. Plots of marginal and conditional residuals will be used for model diagnostics and assessment. Similar diagnostic procedures will be used for the linear regression models.

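### The 12-week analysis of CNI levels ignores CNI dose, although levels are reported so that the dose can be adjusted, and the SAP does not say whether tacrolimus and cyclosporine are modelled separately or on what scale

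*SAP*

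**What the plan says.** **Outcome.** SAP secondary objective 2.2 concerns the acute and chronic effect of dapagliflozin on "Calcineurin inhibitors (CNI) levels, a class of immunosuppressants measured by tacrolimus or cyclosporine". Outcome 2.2 adds only that "CNI levels will be measured by tacrolimus or cyclosporine levels". No unit, transformation, drug-specific analysis or dose normalisation is given.

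**Model.** For secondary objectives 2.2 to 2.10 the SAP states: "The same models described in the analysis of primary objective 1.1 will be completed for each of the different outcomes". In analysis 1.1, "The covariates will include the visit and treatment-by-visit interaction", and for the chronic effect "the vector of outcomes will include the baseline and 12-week values" (Visits 3 and 9). The closing paragraph on general model assumptions adds that "a participant-level random intercept will be included". Neither CNI dose nor CNI drug enters the model. The SAP's baseline medication list (ACEi, ARB, diuretic, statin) omits CNIs, and no summary of CNI dose changes is planned.

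**Dose feedback.** Protocol 6.1 has CNI levels monitored throughout and reported to the "primary transplant nephrologist within 24 hours for CNI dose adjustments", as needed. Section 9.1.2 repeats this for all CNI results. Section 6.2 discourages dose changes for diuretics and vitamin-D analogues, not for CNIs. Section 5.2 excludes only patients who started or stopped an immunosuppressant in the month before screening.

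**Hypothesis.** Protocol 3.3 expects "no clinically significant changes in CNI levels", without a margin.

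**The concern.** A drug level that clinicians steer towards a target is a poor measure of an interaction. If dapagliflozin raised or lowered CNI exposure per milligram, the treating nephrologist might change the dose, and the week-12 level would move back towards where it started. The signal would then sit in the dose, which the SAP does not analyse.

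This matters because the expected result is no change. Without a margin, a non-significant difference in week-12 levels could be read as confirming that expectation when it partly reflects successful dose adjustment. The existing support cited in the protocol is a series of 10 patients (Protocol 2.5 and 6.1), so this placebo-controlled comparison would carry weight.

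A second, smaller matter is that tacrolimus and cyclosporine are different drugs. The SAP does not say whether they share a model, or whether the level is log-transformed.

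**Working it through.** **Plan's own figure.** The documents contain no sizing for CNI levels. The only sample size is for systolic blood pressure, and it reproduces: 2 × (1.960 + 0.842)^2 × 8^2 / 6.5^2 = 23.8, so 24 per arm and 48 in total. It has no bearing on CNI levels.

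**Step 1: what feedback does to the level.**
- Let dapagliflozin multiply exposure per dose by exp(d), so that log level = log dose + constant + d.
- Protocol Table 2 shows blood sampling at Visits 3, 4, 6 and 9. I assume that CNI levels are taken then; the documents do not list CNI sampling by visit.
- Assume that a fraction g of the deviation is corrected by dose after each reported level.
- At Visit 4 the treatment effect is d. Any earlier level predates treatment, so adjustment based on it is unrelated to arm.
- After Visit 4 the remaining effect is (1-g)d. After Visit 6 it is (1-g)d - g(1-g)d = (1-g)^2 d, which is what Visit 9 sees.
- For log(level / dose) the dose term cancels and d remains at every visit.

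Falls of 20% and 30% are assumed for illustration (d = ln 0.8 = -0.223; d = ln 0.7 = -0.357). The fall seen at Visit 9 is 1 - exp((1-g)^2 d):

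| g (assumed) | (1-g)^2 | true fall 20%: seen | true fall 30%: seen |
|---|---|---|---|
| 0 | 100% | 20.0% | 30.0% |
| 0.25 | 56% | 11.8% | 18.2% |
| 0.5 | 25% | 5.4% | 8.5% |
| 0.75 | 6% | 1.4% | 2.2% |
| 1 | 0% | 0% | 0% |

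**Step 2: the SAP model simulated with every participant on tacrolimus.** All CNI inputs are assumptions: 24 per arm, a true 20% fall, between-person SD of log level 0.3, within-person SD 0.2 or 0.3, and 600 replicates per setting. Each cell gives power for within-person SD 0.2 / 0.3.

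| g | raw level, week 12 | raw level, week 1 | log(level / dose), week 12 |
|---|---|---|---|
| 0 | 81% / 49% | 77% / 49% | 87% / 59% |
| 0.5 | 10% / 10% | 63% / 39% | 86% / 59% |
| 0.75 | 7% / 8% | 56% / 35% | 83% / 55% |

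The simulated mean effect on log level at week 12 is -0.23 at g = 0, about -0.05 at g = 0.5 and about -0.02 at g = 0.75. This agrees with (1-g)^2 d (-0.223, -0.056, -0.014). The mean week-1 effect does not shrink with g. Its power falls somewhat, because dose changes made after Visit 3 add variation unrelated to arm.

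**Step 3: the two drugs.** If they were pooled untransformed, the drug with the higher numerical levels would dominate the variance at both time points. With no dose feedback, a cyclosporine share of 10% to 20% and a concentration ratio of 15 to 25 (all assumed), power for a 30% fall drops from 83-99% (tacrolimus only) to 17-50%. For a 20% fall it drops from 49-81% to 9-26%. With no cyclosporine users there is no loss. The documents give neither the share nor the ratio.

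**The case against.** **Pooling is not stated.** A reader might infer from the word joining the two drugs that they form one untransformed outcome. The SAP does not say so. It uses the same shorthand for lists that can only be separate outcomes, such as catecholamines with heart rate, or HbA1c with fasting glucose, and it fits models for each of the different outcomes. Residual plots are also planned, and these might reveal a mixture of two scales, although no remedy is specified. This objection stands: the supported statement is that the SAP is silent.

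**The week-1 comparison.** A reader might infer that the analysis would favour no change whatever the truth. It would not. Feedback caused by dapagliflozin cannot come before the first on-treatment level, so the Visit 3 to Visit 4 effect is not masked. This stands and confines the point to week 12.

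**Adjustment is conditional.** Both protocol passages make dose changes depend on need, so a moderate shift may prompt none, and full correction is an extreme. This stands, which is why g = 0 is in the range. Protocol 9.2, which blinds study personnel to laboratory results, also has to be reconciled with the 24-hour CNI reporting. The two passages specific to CNI are nevertheless explicit.

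**A different question.** The hypothesis concerns levels under usual care, whereas level per dose is a pharmacokinetic measure. This is fair, and it argues for reporting both. It does not justify leaving dose out, because an unchanged level cannot otherwise be told apart from a corrected one.

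**Other safeguards.** Levels are monitored, and acute rejection and kidney injury are counted by arm. The protocol also reports no known interaction. That limits the risk to participants and makes a large effect less likely, but it does not repair the comparison.

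**Conclusion.** The point holds for the 12-week comparison. As written, the SAP analyses a level that may have been corrected by dose and makes no use of the dose, so a real change in exposure per dose can be understated or missed. This is true even if every participant takes tacrolimus. The share of the effect left at Visit 9 runs from 100% (no adjustment) through 56%, 25% and 6% (g = 0.25, 0.5, 0.75) to none (full correction). These figures assume proportional correction after two on-treatment levels. The power figures rest on further inputs that the documents do not give, so they illustrate the direction and are not estimates for this trial.

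The second part is one of specification: drug separation and scale are not stated. Loss of precision from pooling is conditional both on pooling and on a material cyclosporine share, and neither is established. The SAP should be amended on both counts, but this is a secondary outcome with nominal p-values and the primary analysis is unaffected.

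**What to change.** In SAP outcome 2.2 and its analysis:

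1. Model tacrolimus and cyclosporine separately, or together with a CNI-drug term, on the log scale. If there are few cyclosporine users, describe them only.
2. Add an analysis of log(level / current daily dose) at Visits 3, 4 and 9 with the structure of model 1.1. Report the treatment ratio with its 95% confidence interval for the acute and the chronic contrast.
3. Tabulate CNI dose changes by arm.
4. Keep the level analysis, labelled as exposure under usual care.

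**Cost.** This takes SAP wording, a little more analysis, and the CNI dose at three visits from the medication record, or a CRF item if it is not captured. Protocol Table 3 is not fully legible in the available copy, so I do not claim that dose is uncollected. Level per dose assumes that level is roughly proportional to dose, and it needs the dose recorded accurately. Clinical management does not change.
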